4.3.7 Clinical Laboratory Values

Clinical laboratory values collected as below or above a limit of quantitation (e.g. containing "<" or ">" in the laboratory value) will be analyzed according to the numeric value associated with the ">" or "<" symbol.

Confidential

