### **1.2 Chemotherapy-Induced Thrombocytopenia**

Chemotherapy-induced thrombocytopenia (CIT) is a common toxicity of myelosuppressive chemotherapy. Occurrence of thrombocytopenia has the potential to create significant complications. At platelet counts  $<10,000/\mu L$ , spontaneous bleeding risk is increased. At platelet counts  $<50,000/\mu L$ , procedures are often complicated by bleeding. At platelet counts  $<100,000/\mu L$ , chemotherapy is administered with caution for fear of worsening the thrombocytopenia and increasing the risk of bleeding.

Clinicians' responses to thrombocytopenia in a cancer patient vary: reduction of the dose intensity of chemotherapy is common, more effective regimens with thrombocytopenic toxicity may be avoided, and treatment may even be precluded. Platelet transfusions are often the only treatment; however, platelet transfusions create the additional risk of transfusion reactions or infections, and may lead to the development of platelet refractoriness with repeated platelet transfusions. The latter importantly eliminates platelets as an option for future emergent needs in these patients during their chemotherapy regimen or for other emergent conditions that may develop.

The incidence, severity, and duration of thrombocytopenia vary with the chemotherapy regimen. Kuter, 2015 provides an overview of the reported frequencies of severe thrombocytopenia (Grade 3 =  $25,000$  to  $<50,000/\mu L$ , Grade 4  $\leq 25,000/\mu L$ ) associated with various chemotherapy regimens.

The reasons that some patients experience more severe or prolonged thrombocytopenia after chemotherapy are not well understood and can be difficult to predict. The mechanisms by which chemotherapy regimens result in thrombocytopenia also differ and include the following:

- Alkylating agents such as busulfan affect pluripotent stem cells;
- Cyclophosphamide spares hematopoietic stem cells, but affects later megakaryocyte progenitors;
- Bortezomib has no effect on stem cells or megakaryocyte maturation but does inhibit nuclear factor kappa B, a critical regulator of platelet shedding; and
- Chemotherapy may enhance platelet clearance by immune mechanisms, as occurs with fludarabine.

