4.1.2 Visit Windows

No formal visit windowing will be conducted. For by-visit/by-cycle tabular summaries, the scheduled visits or actual chemotherapy cycles will be used in the analyses. The exception to this is for nadir platelet counts; both scheduled and unscheduled platelet counts will be considered for designation of the nadir value within a cycle.

For analyses considering the worst post-baseline grade (laboratory shift tables) or post-baseline liver tests, all post-baseline values will be considered.

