4.3.2 Platelet Counts

Platelet counts are collected at local laboratories for eligibility and efficacy assessments. Platelet count is also included in the hematology panel sent to the central laboratory as a safety evaluation. For the efficacy analyses, only platelet counts assessed by the local laboratories will be included in the calculations and summaries. For the safety analyses, only platelet counts assessed by the central laboratory will be included in the summaries.

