8.3 Other Efficacy Analysis

The other efficacy endpoints include the following during the period after post-chemotherapy IP treatment in Cycle X+1 through Chemotherapy Day of Cycle X+2:

- Proportion of subjects who do not have a chemotherapy dose reduction that is $\geq 15\%$ due to thrombocytopenia;
- Proportion of subjects who do not have a chemotherapy delay that is ≥ 4 days due to thrombocytopenia;
- Proportion of subjects with a pre-defined post-baseline nadir platelet count (i.e., subjects with the lowest platelet count <10 , <25 , <50 , <75 , <100 , and $\geq 100 \times 10^9/L$ at any time);
- Proportion of subjects achieving a pre-defined post-baseline maximum platelet count (i.e., subjects with the highest platelet count ≤ 400 , >400 , and $>600 \times 10^9/L$ at any time).

Confidential

Categorical variables (eg, proportion) will be summarized and analyzed in the similar manner as the primary efficacy endpoint. If the data is sparse where the approximative methods cannot be applied, the Fisher's Exact test will be used instead.

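### A platelet result reported as `<n` or `>n` is analysed at n, so under the strict limits in SAP 8.3 it is classed against its own inequality whenever n equals a category limit

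*SAP*

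**What the plan says.** SAP 4.3.7 sits under the general data handling conventions. Its subject is "Clinical laboratory values collected as below or above a limit of quantitation", and such values "will be analyzed according to the numeric value associated with the" symbol. So `<n` and `>n` are both analysed as n. No test is exempted.

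SAP 4.3.2 deals with platelet counts specifically. It sets the source ("For the efficacy analyses, only platelet counts assessed by the local laboratories will be included in the calculations and summaries") but gives no rule of its own for results reported with an inequality sign. SAP 4.1.2 adds that "both scheduled and unscheduled platelet counts will be considered for designation of the nadir value within a cycle".

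SAP 8.3 lists two sets of platelet categories among the other efficacy endpoints:

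- Nadir: "subjects with the lowest platelet count <10 , <25 , <50", then below 75, below 100, and at least 100 × 10⁹/L.
- Maximum: at most 400, above 400, and above 600 × 10⁹/L.

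These proportions are to be analysed much as the primary endpoint is, with Fisher's Exact test if the data are sparse.

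**The concern.** A laboratory that reports `<10` has stated that the count is below 10. If the analysis value is 10, the table says the count was not below 10, and the table contradicts the listing it came from. The same happens at the upper end with `>400` and `>600`.

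The limits involved carry some meaning. Protocol 1.2 says that below 10,000/µL, which is 10 × 10⁹/L, "spontaneous bleeding risk is increased". A count above 400 × 10⁹/L is the point at which Protocol 3.1.2 has dosing stopped temporarily. Because the proportions are tested as well as displayed, a misclassified subject would also enter a p-value. In a category with few events, one or two subjects can be a large share of them.

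**Working it through.** The plan states no figure to reproduce, so the check is to apply one rule and then the other.

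**Inputs**

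- Substitution: `<n` and `>n` become n (SAP 4.3.7).
- Nadir categories: <10, <25, <50, <75, <100, ≥100 (SAP 8.3).
- Maximum categories: ≤400, >400, >600 (SAP 8.3).
- Planned arms: 80 avatrombopag, 40 placebo (SAP 3.3).
- Local reporting limits: not given in either document. Assumption: they may lie anywhere from `<1` to `<50` at the low end, or from `>400` to `>1000` at the high end.

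**Step 1: low end**

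| Reported | Analysed as | In <10? | In <25? | In <50? |
|---|---|---|---|---|
| `<1`, `<2`, `<5` | 1, 2, 5 | yes | yes | yes |
| `<10` | 10 | **no** | yes | yes |
| `<20` | 20 | no | yes | yes |
| `<25` | 25 | no | **no** | yes |
| `<50` | 50 | no | no | **no** |

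The bold entries contradict the reported result, and each occurs only where the limit equals a category limit. For `<20` the entry under <10 is not a contradiction, because the report does not say whether the count was below 10. The nadir categories overlap, so a `<10` subject missing from the first is still counted in every wider one.

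**Step 2: high end**

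| Reported | Analysed as | In ≤400? | In >400? | In >600? |
|---|---|---|---|---|
| `>400` | 400 | **yes** | **no** | no |
| `>600` | 600 | no | yes | **no** |
| `>1000` | 1000 | no | yes | yes |

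**Step 3: weight of one subject**

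One subject divided by the planned arm size gives 1/40 = 2.5 percentage points on placebo and 1/80 = 1.25 on avatrombopag. This is the leverage of a single reclassified subject. It is not an estimate of how many there will be.

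**Step 4: other endpoints**

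- Primary endpoint (SAP 8.1): transfusion, dose reduction and delay. No platelet limit enters.
- Duration of severe thrombocytopenia (SAP 8.2.1): the limit is 50, and 10 < 50, so a `<10` result still counts. By the same logic only a result reported as exactly `<50` would be contradicted.
- Change in nadir (SAP 8.2.1): a `<10` result enters as 10 in place of some lower value, so it is too high by at most 10 × 10⁹/L. This is a numeric convention and contradicts no reported inequality.

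**The case against.** The strongest reply is that the triggering fact is absent. Neither document gives a local reporting limit for platelets or says that any laboratory reports `<10`, `>400` or `>600`. That stands, and the point must stay conditional. A reader might infer that the below-10 count is understated; the documents show only that it would be if such results occur.

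The second reply concerns scope. Platelet counts have their own subsection (SAP 4.3.2), and SAP 9.3 uses similar wording for central-laboratory safety data, so 4.3.7 could be read as a safety convention. Against that, 4.3.7 is placed among the general conventions without exemption, and Protocol Appendix B lists platelets under hematology. The text can be read either way. If 4.3.7 does not govern local platelet counts, the SAP has no rule for a `<10` efficacy result, and the same added text fills that gap.

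The third reply is about weight. These are other efficacy endpoints, outside the hierarchy in SAP 8.2.2, and clinically relevant bleeding is measured directly as a key secondary endpoint. That also stands. It makes this a wording correction and not a threat to the trial's conclusions.

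**Conclusion.** The two SAP rules, read together, class a result against its own inequality whenever the reporting limit equals a category limit. The conclusion rests on two assumptions: that 4.3.7 applies to local platelet counts, and that at least one local laboratory reports at such a limit. If both hold, the effect is 2.5 or 1.25 percentage points per affected subject in the nadir or maximum-count proportions. If either fails, this contradiction does not arise.

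Three stronger readings are tempting and are not supported:

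- *That the lowest category is the decisive one clinically.* Protocol 1.2 is background and says only that spontaneous bleeding risk rises there. No trial decision is tied to the category.
- *That the error favours avatrombopag.* No direction is established. If deep nadirs are concentrated on placebo, undercounting them would shrink the apparent benefit, which is conservative for an efficacy claim.
- *That differing limits across approximately 75 sites bias the comparison, and that classifying by inequality cures this.* The documents show no difference in limits between arms in a randomized, double-blind trial. A `<20` result also cannot be placed against the below-10 limit under any wording, whereas a laboratory reporting 8 can be classed, so the same true count may still be handled differently by site.

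The point is minor and worth correcting because the correction is so cheap.

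**What to change.** Add to SAP 4.3.7:

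> For classification against a threshold, a result reported as <n is treated as below n and a result reported as >n as above n; the numeric limit is used only in numeric analyses (summaries, change-from-baseline models, plots). Results whose reporting limit does not determine the category (eg, <20 against the <10 cut-off) are flagged in the listing. This applies to local platelet counts used for efficacy.

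With this text `<10` counts in below-10 and every wider nadir category, `>400` counts as above 400, and `>600` counts as above both 400 and 600. The nadir-change model keeps its present numeric rule. The last sentence settles the scope question.

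The cost is a few lines of SAP text and a category derivation that reads the result as reported. Design, data collection and alpha are unchanged. It should be settled before unblinding so that the coding of a sparse category is not decided with the results in view.

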4.4 Treatment Groups

Data displays for the Double-Blind Treatment period/Observational period will have columns for avatrombopag 60 mg dose and placebo groups, unless otherwise specified. Data displays for the optional OLE period will have 3 columns: subjects randomized to avatrombopag 60 mg dose, subjects randomized to placebo, and a total column (all subjects in the optional OLE period receive avatrombopag 60 mg). Data displays for the entire study will include subjects randomized to avatrombopag 60 mg only.

Data listings will generally include Subject ID, Age/Sex/Race, and an indicator of whether the applicable record occurred during the Screening, Double-Blind, Observational, or OLE periods.

5. Study Patients

5.1 Disposition of Patients

Disposition will be summarized by treatment group and overall for the FAS population.

A summary table will include the total number of subjects screened and randomized. The number and percentage of subjects in each analysis set will be presented by treatment group.

The summary table will also contain the number and percentage of subjects who completed the Double-Blind/Observational period, discontinued the study during the Double-Blind/Observational period (along with reason), entered the OLE period, completed the OLE period, and discontinued the study during the OLE period (along with reason).

Details of "Other" reason for discontinuation will be included in a disposition listing.

A separate table summary and listing will also indicate the reasons subjects were screen failures for the Double-Blind period as well as the reasons subjects did not enter the OLE period.

5.2 Protocol Deviations

The number and percentage of subjects with major protocol deviations will be summarized by category by treatment group and overall for the FAS. Details of the major protocol deviations will be provided in a listing.

The number and percentage of subjects who are excluded from the PPS will be summarized by treatment group, along with reasons for exclusion. Subjects excluded from PPS will also be presented in a data listing.

5.3 Inclusion and Exclusion Criteria Not Met

Details of inclusion/exclusion criteria not met for subjects in the FAS will be provided in a listing. The listing will separately note whether the inclusion/exclusion criteria not met was for the Double-Blind period or for the OLE period.

5.4 Randomization

For subjects in the FAS, a listing will be provided which details randomization information (including treatment group, date/time, number of eligible

Confidential

chemotherapy agents) as collected in the Interactive Web Response System (IWRS), and kit number of the study drug assigned.

6. Demographic and other Baseline Characteristics

Demographics and Baseline Characteristics will be summarized for subjects in the FAS for the Double-Blind period. If necessary, summaries will be repeated for subjects in the PPS.

6.1 Demographics and Baseline Characteristics

Descriptive statistics with respect to subject characteristics at baseline will be displayed by treatment group for the FAS. The variables to be summarized are:

Demographics

- Age at enrollment (years)
- Age group at enrollment: <65 years, 65-<75 years, 75-<85 years, 85+ years
- Sex
- Race
- Ethnicity
- ECOG Performance Status
- Region (United States, Europe, China)

Baseline subject characteristics

- Height (cm)
- Weight (kg)
- Body Mass Index (BMI) (kg/m²)
- Baseline platelet count (10⁹/L) (defined as the lowest platelet count collected during the qualifying period in Cycle X and prior to first dose of study drug)
- Platelet count prior to study treatment start (i.e., the last platelet count collected prior to the first dose of study drug)
- Number of eligible chemotherapy agents recorded in IWRS

A listing of demographic and baseline characteristics will also be provided.

6.2 Medical and Surgical History

Medical and surgical history will be coded using the Medical Dictionary for Regulatory Authorities (MedDRA) version 23.0. The coding version may be updated prior to database lock if a newer version is available.

Medical and surgical history will be tabulated by MedDRA System Organ Class (SOC) and Preferred Term (PT) for the FAS. Subjects with more than one medical history event in a SOC or PT will only be counted once per SOC or PT.

Medical history details will also be provided in a data listing.

6.3 Oncology History

Descriptive statistics with respect to oncology history and cancer characteristics will be displayed by treatment group for the FAS. The variables to be summarized are:

Confidential

- Primary Cancer Diagnosis: Ovarian, Non-small cell lung cancer, Small cell lung cancer, Bladder cancer
- Stage (I, II, III, IV)
- Time since diagnosis (years), defined as (Date of randomization – Date of Diagnosis)/365.25
- Cycle length of current regimen: 21-day or 28-day
- Cycle of Chemotherapy at Study Entry, both continuous and categorical
- Prior Surgery for Current Cancer (Yes/No)
- Prior Radiation for Current Cancer (Yes/No)
- Prior Chemotherapeutic Regimens for Current Cancer (Yes/No) and number of prior chemotherapy regimens (1 or 2)
- Number of Eligible Chemotherapy Agents recorded on eCRF (1, 2, 3, or 4)

A listing of oncology history will be provided.

7. Prior and Concomitant Treatment

Prior and Concomitant medications will be classified according to the World Health Organization (WHO) Drug Dictionary (March 2020, B3). The coding version may be updated prior to database lock if a newer version is available. Medications will be coded per the Anatomical Therapeutic Classification (ATC). All medications will be documented from the time of informed consent up to the Follow-up visit.

Prior medications are those which start and stop before the first day of study treatment in the Double-Blind period. Concomitant medications for the Double-Blind/Observational period are those which start on or after the first day of study treatment and prior to the first dose of the study drug in the OLE period. A medication which begins before the start of study treatment in the Double-Blind period and continues into the Double-Blind period will be considered as concomitant for the Double-Blind/Observational period.

Concomitant medications for the OLE period are those which begin prior to the OLE period and continue into the OLE period or those which start on or after the first day of study treatment in the OLE period.

Tabular summaries will display the number and percentage of subjects with at least one medication in ATC Level 2 and preferred term categories and overall. Subjects who have taken a medication more than once will only be summarized once per ATC Level 2 or preferred term.

The tabular summaries to be provided are as follows:

- Prior Medications
- Concomitant Medications (Double-Blind/Observational period)
- Concomitant Medications (OLE period)
- Concomitant Medications taken as rescue for a bleeding event (Double-Blind/Observational period)
- Concomitant Medications taken as rescue for a bleeding event (OLE period)

An overall listing of medications will be provided. The listing will designate whether a medication is considered prior or concomitant. A separate listing will also be produced for concomitant medications taken as rescue for a bleeding event.

Confidential

A data listing for the concomitant radiation therapy procedures will also be provided.

Chemotherapy agents that the subjects received during Cycle X + 1 will be summarized by preferred name for FAS. The study chemotherapy data will also be provided in a data listing.

8. Efficacy Evaluation

All primary and secondary efficacy endpoints will be analyzed using the FAS.

8.1 Primary Efficacy Analysis

The primary efficacy endpoint is the proportion of responders who meet all of the following criteria during the period after post-chemotherapy IP treatment in Cycle X+1 through Chemotherapy Day of Cycle X+2:

- Not requiring a platelet transfusion;
- Not requiring a chemotherapy dose reduction by $\geq 15\%$ due to thrombocytopenia; and
- Not requiring a chemotherapy delay by ≥ 4 days due to thrombocytopenia.

Chemotherapy Day is defined as the latest among Day 1 to 3 of the subject's chemotherapy regimen (eg, if chemotherapy is given on Day 1 and Day 2, Day 2 will be the Chemotherapy Day). For subjects whose chemotherapy is on an intermittent schedule (eg, Days 1, 8, 15), Day 1 will be the Chemotherapy Day.

If subjects had no post-chemotherapy IP dosing in Cycle X+1, the assessment period of the primary efficacy endpoint will start from the day after Chemotherapy Day in Cycle X+1 through Chemotherapy Day in Cycle X+2.

If subjects had any post-chemotherapy IP dosing in Cycle X+1, the assessment period of the primary efficacy endpoint will start from the day after post-chemotherapy IP dosing in Cycle X+1 through Chemotherapy Day in Cycle X+2.

If the information on platelet transfusion or chemotherapy dose reduction or delay is missing (eg, due to early drop-out), the subject will be treated as a non-responder in the primary analysis.

The primary efficacy endpoint will be tested between avatrombopag and placebo using the Cochran-Mantel-Haenszel (CMH) 2-sided test at $\alpha=0.05$, adjusting for number of eligible chemotherapy agents as collected in the IWRS (1 or ≥ 2 permissible chemotherapy agents). The numbers and percentages of responders in each treatment group with the associated unadjusted exact (Clopper-Pearson) 95% CI, and the difference in proportion of responders between avatrombopag and placebo with the associated unadjusted exact (Clopper-Pearson) 95% CI will be calculated. The primary analysis will be performed based on the FAS and repeated on the PPS as a supportive analysis.

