##### **10.2.1.1 Primary efficacy analysis**

The primary efficacy endpoint is the proportion of responders who meet all of the following criteria during the period after post-chemotherapy IP treatment in Cycle X+1 through Chemotherapy Day of Cycle X+2:

- Not requiring a platelet transfusion;
- Not requiring a chemotherapy dose reduction by  $\geq 15\%$  due to thrombocytopenia; and
- Not requiring a chemotherapy delay by  $\geq 4$  days due to thrombocytopenia

Subjects without sufficient data for the determination of response status (ie, responder versus non-responder) will be treated as non-responders in the analysis. Every effort should be made during the conduct of the study to limit the extent of missing data with subjects who prematurely discontinue IP but remain in the study for collection of data, unless the subject withdraws consent.

The treatment effect on the primary efficacy endpoint will be tested between avatrombopag and placebo using the Cochran-Mantel-Haenszel test, adjusting for number of chemotherapy agents (1 or  $\geq 2$  permissible chemotherapy agents [nucleoside analog, including gemcitabine and fluorouracil; carboplatin or cisplatin; anthracycline; or alkylating agent]). The numbers and percentages of responders in each treatment group, the associated 95% confidence intervals (CI), and the 95% CI for the difference between avatrombopag and placebo will be calculated. The primary analysis will be performed based on the FAS and repeated on the PPS. Other sensitivity analyses of the primary efficacy endpoint may be performed as appropriate.

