### **10.2.4 Sample Size Determination**

Assuming there is a 40% response rate in the active group and 10% in the placebo group, and using a 2:1 randomization, a 10% premature termination rate, and 90% power with 2-sided alpha = 0.05, the sample size is 120 subjects (80 active subjects and 40 placebo subjects).

The assumptions for the response rates for the null and alternative hypotheses were based upon results from a study in CIT completed with oprelvekin (Neumega, Pfizer). The study design for oprelvekin was similar in that subjects were randomized to active or placebo following occurrence of severe thrombocytopenia (platelet count  $\leq 20 \times 10^9/L$  in a previous cycle [Cycle X]). The primary endpoint of the study assessed the ability of oprelvekin to eliminate the need for platelet transfusions. In the placebo group (n=30), 93% of subjects required a platelet transfusion (7% responder rate) and 72% of active subjects (n=29) required a platelet transfusion (28% responder rate). The responder rates assumed for the null and alternative hypotheses in the AVA-CIT-330 study were based upon the responder rates in this similarly designed study with an assumption for a slightly higher response rate due to the inclusion of subjects with a platelet count in Cycle X of  $< 50 \times 10^9/L$ , rather than  $\leq 20 \times 10^9/L$ .

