- Proportion of subjects who do not have major or non-major clinically relevant bleeding during the period after post-chemotherapy IP treatment in Cycle X+1 through Chemotherapy Day of Cycle X + 2

Subjects will be considered to NOT have major or non-major clinically relevant bleeding if no bleeding events were reported on the ISTH Non-surgical Bleeding Assessment CRF page that were classified as "Major Bleeding" or "Non-major clinically relevant bleeding" from the day after the last post-chemotherapy IP in Cycle X + 1 through the Chemotherapy Day in Cycle X+2. If information on the bleeding events is missing, subjects will be assumed to have had major or non-major clinically relevant bleeding during that period.

- Proportion of subjects who do not receive platelet transfusion during the period after post-chemotherapy IP treatment in Cycle X+1 through Chemotherapy Day of Cycle X + 2

Subjects will be considered to have not required a platelet transfusion if subjects did not require a platelet transfusion after taking the last post-chemotherapy IP in Cycle X + 1 through the Chemotherapy Day in Cycle X + 2. If information on platelet transfusion is missing, subjects will be assumed to have had a platelet transfusion during that period.

The categorical variables (eg, proportion) will be summarized and analyzed in the same manner as the primary efficacy endpoint. If the data is sparse where the

Confidential

approximative methods cannot be applied, the Fisher's Exact test will be used instead.

For continuous variables (eg, change from baseline in platelet count, duration of severe thrombocytopenia), the normality assumption of an analysis of covariance will be evaluated analytically using the Shapiro-Wilk test and visually using the residual plot.

Plots will be created displaying platelet count values over time separately for the Double-Blind/Observational period, the OLE period, and the entire study.

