8.6 Subgroup Analyses

The primary efficacy analysis will be repeated for the following subgroups:

- Age (< 65 years, $65- < 75$ years, $75- < 85$ years, $85+$ years)
- Sex
- Race (White vs Non-White)
- Number of eligible chemotherapy agents (1 vs ≥ 2)
- Tumor type (ovarian cancer, lung cancer, bladder cancer)
- Previous chemotherapy regimens (0 vs 1 vs 2)
- Region (United States, Europe, China)

Confidential

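### The SAP gives the difference in responder rates a Clopper-Pearson interval, a one-proportion method, so the primary effect's confidence interval is undefined and also unstratified

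*SAP*

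**What the plan says.** SAP 8.1 compares the arms on the primary endpoint, "tested between avatrombopag and placebo using the Cochran-Mantel-Haenszel (CMH) 2-sided test", "adjusting for number of eligible chemotherapy agents as collected in the IWRS". The stratum has two levels: one agent, or two or more.

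The next sentence sets the intervals. For each arm it asks for "The numbers and percentages of responders in each treatment group with the associated unadjusted exact (Clopper-Pearson) 95% CI". For the comparison it asks that "the difference in proportion of responders between avatrombopag and placebo with the associated unadjusted exact (Clopper-Pearson) 95% CI will be calculated". The same one-sample method is thus named for two different quantities.

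Protocol 10.2.1.1 says only that "the 95% CI for the difference between avatrombopag and placebo will be calculated", and the synopsis says the same. SAP 8.4 adds a Fisher's exact test and an observed-case repeat, but no interval method.

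The wording carries further. For the binary key secondary endpoints, SAP 8.2.1 states: "The categorical variables (eg, proportion) will be summarized and analyzed in the same manner as the primary efficacy endpoint". SAP 8.3 treats the other proportions similarly, and SAP 8.6 begins: "The primary efficacy analysis will be repeated for the following subgroups".

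**The concern.** Clopper-Pearson inverts the two tails of a single binomial distribution. A difference of two proportions has a second unknown, the underlying rate, and the method gives no rule for handling it. The SAP sentence is the only specification of the interval, and it cannot be carried out.

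The word exact suggests that an exact unconditional interval may have been meant. Such an interval depends on the statistic used to order the outcomes (raw difference or score), and none is named.

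Separately, the interval is unstratified while the deciding test is stratified, so estimate and test do not correspond.

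At stake is the reported effect size. If the method is chosen after unblinding, someone picks among intervals that can differ on whether zero is included. An exact interval can also include zero beside a significant primary test.

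**Working it through.** **Inputs.** From Protocol 10.2.4 and SAP 3.3: 40% against 10%, 2:1 allocation, 80 and 40 patients, two-sided 0.05, 90% power, 10% premature termination. From SAP 8.1: CMH test stratified by number of agents. The documents give no stratum sizes or stratum rates, so anything stratified below is an assumption.

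**1. The plan's own figure.** The pooled normal approximation needs 31.63 placebo patients, or 36.46 with continuity correction. Total: 3 × 36.46 = 109.4; 109.4 / 0.9 = 121.5, within two patients of 120. With 120 × 0.9 = 108 evaluable (72 and 36), corrected power is 89.5%. The sample size is not in question.

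**2. Planned result, 32/80 against 4/40 (difference 30 points).** Clopper-Pearson works per arm: 29.2% to 51.6% and 2.8% to 23.7%. For the difference, possible readings are:

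| Method | 95% limits (points) |
|---|---|
| Clopper-Pearson limits subtracted | 5.5 to 48.8 |
| Exact unconditional, raw difference | 10.6 to 47.9 |
| Clopper-Pearson limits, square-and-add | 12.6 to 43.6 |
| Exact unconditional, score | 12.7 to 43.9 |
| Newcombe | 13.5 to 42.5 |
| Miettinen-Nurminen | 13.9 to 43.2 |
| Wald | 15.8 to 44.2 |

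All exclude zero. Even the exact score interval needs a convention: its tail probability is not monotone and crosses 0.025 near 10.8 and again near 12.7 points.

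**3. A borderline result, 21/80 against 4/40, single stratum.** CMH statistic:

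- observed minus expected = 21 − 80 × 25/120 = 4.333
- variance = 80 × 40 × 25 × 95 / (120² × 119) = 4.435
- chi-square = 4.333² / 4.435 = 4.234, p = 0.040

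Exact one-sided p-values at zero difference, maximised over the common rate, are 0.053 (raw) and 0.026 (score), both above 0.025. The intervals are −3.3 to 35.0 (raw), −0.1 to 29.5 (score) and 0.9 to 29.0 (Miettinen-Nurminen).

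**4. How often test and interval conflict.** Enumerating all 81 × 41 outcomes, the share of CMH-significant trials whose exact interval includes zero is:

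| True rates | Raw | Score |
|---|---|---|
| 40% / 10% (planned) | 3.65% | 3.2% |
| 28% / 7% (transfusion-free rates of the oprelvekin study cited in Protocol 10.2.4; not a planning assumption here) | 27% | 11% |

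Two-stratum simulations at about 40%/10% overall (smaller stratum 10% to 50% of patients, equal or moderately different rates) gave 3.6% to 4.1% (raw) and 3.2% to 3.7% (score).

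**5. The stratification mismatch alone.** An unadjusted Newcombe interval conflicted with CMH in 0.01% to 0.7% of significant trials, and in 1.4% under an extreme assumed factor. This part is small.

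**6. Why the proposed interval agrees with the test.** In stratum h, let the arm sizes be n₁ and n₂, N = n₁ + n₂, m responders, pooled rate p = m/N, and Mantel-Haenszel weight w = n₁n₂/N. Then w × (difference) equals observed minus expected in the CMH numerator. The Miettinen-Nurminen variance at zero difference is p(1−p)(1/n₁ + 1/n₂) × N/(N−1). Multiplied by w² it becomes n₁n₂m(N−m) / [N²(N−1)], the CMH variance. Summing over strata, the two statistics are identical. Check on step 3: difference 0.1625, standard error √(0.16493 × 0.0375 × 120/119) = 0.0790, z = 2.058, z² = 4.234. Simulation showed no conflict in either direction; the largest gap in z was 1e-12.

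**The case against.** The strongest reply is that this is mainly a labelling slip. The SAP says the interval is exact and unadjusted, so its class is known and only the construction is missing. The separate mock tables mentioned in SAP 11 might name it. That narrows the intent, but step 2 shows that the remaining choice moves the limits, and neither document makes it.

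The lack of stratification is openly declared, the protocol does not ask for a stratified interval, and an unadjusted difference beside a stratified test is a legitimate description. This stands as far as it goes: the mismatch is a minor part of the concern.

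The 3.2% to 3.65% conflict rates compare an exact interval with an asymptotic test, and would be the same had an exact method been named correctly. That is true. They measure the cost of the most natural reading of the sentence; the cost of the ambiguity itself is the spread between readings. The 28%/7% figures come from a transfusion-only endpoint in patients with lower counts and should carry no weight in grading the point.

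**Conclusion.** The concern holds. The SAP assigns a one-sample method to a two-sample quantity in the primary analysis paragraph, and nothing else in either document supplies a usable method. The per-arm intervals are correct.

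The effect is confined to the reported difference and its interval, for the primary endpoint and for the secondary, other and subgroup proportions that inherit the wording. The primary decision and the testing hierarchy are untouched. If the planned effect appears, every reading excludes zero; disagreement arises near significance, in roughly 3% to 4% of CMH-significant trials at the planned rates if an exact interval is used. The single-stratum figures rest only on 80 and 40 patients and the stated rates; the stratified ones rest on assumed stratum sizes and rates. It should be corrected, but it does not threaten the trial's conclusion.

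**What to change.** Amend the sentence in SAP 8.1 before database lock and unblinding:

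- Keep Clopper-Pearson for each arm's responder rate.
- For the difference, report the Mantel-Haenszel-weighted risk difference over the IWRS stratum with a stratified Miettinen-Nurminen score 95% interval using the same weights. State that the CMH test has no continuity correction.
- Apply the same wording to SAP 8.2.1, 8.3 and 8.6. Within the subgroups defined by number of agents it reduces to the single-stratum form.
- Where Fisher's test replaces CMH for sparse data, name an exact unconditional interval, its statistic (score) and the inversion convention. State that it need not agree with Fisher's test: at 40%/10% about 2.6% of Fisher-significant trials would have a score interval including zero. For example, 24/80 against 5/40 has Fisher p = 0.042 and a lower limit of −0.1 points.

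The cost is a short text change and the matching program change. The interval is asymptotic: simulated coverage was 94.7% to 95.2% with a common difference, including a stratum of only 4 against 2 patients, and 96% to 98% when effects differed strongly between strata. A stratified Newcombe interval is an acceptable alternative, though it conflicted with CMH in 0.02% to 1.4% of significant trials. If an unadjusted exact interval is preferred, naming its statistic and convention would remove the ambiguity but not the possible conflict with CMH, so it fits better as supportive.
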